[name]

NCT04011436

Therapeutic Effect of Two Muscle Strengthening Programs in Patients with Patellofemoral Pain Syndrome

**Therapeutic Effect of Two Muscle Strengthening
Programs in Patients with Patellofemoral Pain
Syndrome from Bogota, Colombia.
Experimental Study, Clinical Controlled Trial.**

NCT: 04011436

Date of creation: July 1, 2018.

PROCESSING AND DATA ANALYSIS.

For the classification and verification of the information, the database was refined by recoding and labeling the variables necessary for the analysis, in addition, the variables that required it were converted to alphanumeric format and the review of extreme non-plausible data was performed. For the continuous variables in which two attempts were made as balance and plate a new variable was generated with the average of the measurements and in this way obtain the final result for the analyzes.

Univariate Analysis

The report of absolute and relative frequencies was made; the qualitative variables were presented in proportions and 95% confidence intervals. The normality of the continuous variables was evaluated by scatter plots (histograms, Kernel density and Q-Norm) and the numerical test of Shapiro-Wilk, and according to their distribution they were reported as means and standard deviations, when they had a distribution normal, or on the contrary, as medians and interquartile ranges.

Bivariate Analysis

In the bivariate analysis, a comparison of each of the Kujala test domains was initially performed to assess pain in the baseline, assessing the differences between the intervention groups using the chi-square or Fisher's exact tests. Additionally, the Spearman correlation coefficient was used to evaluate the relationship between two continuous variables, such as the Q angle and the anterior knee pain, evaluating the correlation in a marginal and conditioned way to each of the treatment groups.

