Later, to evaluate if there were differences between the groups of treatment after the intervention on the variables of interest, deltas were generated from the Kujala test, EVA, number of squats, Q angle, balance, physical activity and core strength. with iron and trunk extension, evaluating normality by means of graphic and numerical methods. For the analysis of the differences of medians between the groups, taking into account that the outcomes did not present a normal distribution, and assuming the assumption of independence of the variables, we proceeded to use the non-parametric Mann-Whitney U test. Finally, through the Wilcoxon test, intragroup differences were evaluated for strength, pain and physical activity components.

The hypothesis tests were presented in two tails with an alpha of 0.05 and all the analyzes were executed with the statistical program STATA version 14.0.

BASELINE:

Study population

Therapeutic Effect of Two Muscle Strengthening Programs in Patients with Patellofemoral Pain Syndrome

Table 5 describes the general characteristics of the study population at baseline. There were no significant differences between the two intervention groups (A and B), which means that the randomization was adequate; however, in the total score of the Kujala test there was a difference of 12.5 points between the groups, with a lower score for group B (53.0), which indicates better core strength for these patients. Finally, the sex variable was defined as categorical and the rest of the variables as continuous, for which the medians and their respective interquartile range (IR) are reported, taking into account that the variables did not have a normal distribution.

Table 5: Baseline variables of the study population

Variables	Treatment A (n 20) Medium (RI)	Treatment B (n 20) Medium (RI)	Value p ^a
Sex * (Male, Ref)			
Female	90 (65.7-97.6) *	90.0 (65.7-97.6) *	1,000 ^b
Age	32.5 (25.5-38.0)	29.0 (25.0-36.5)	0,569
Initial weight (Kg)	64.6 (55.3-72.4)	62.7 (52.9-68.5)	0.379
Size (cm)	160 (156.5-167.0)	159.5 (154.0-163.0)	0.423
IMC	25.4 (21.5-27.9)	23.8 (22.3-25.2)	0.456
% of fat	35.4 (28.9-40.4)	35.4 (24.5-38.7)	0,714
% muscle	26.9 (24.5-28.9)	26.2 (24.6-29.0)	0.849
Visceral fat	6 (3.5-7.09)	5 (4.0-6.0)	0.433
IPAQ (minutes)	3003 (1116-4638)	1617 (944-6138)	0,588
Pain	7.5 (5.5-9.0)	7.0 (5.5-8.5)	0.764
Kujala total score	65.5 (42.5-72.5)	53.0 (44.5-71.5)	0,892
Q angle			
Straight	19.0 (15.0-20.0)	18.0 (15.0-20.0)	0,557

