Left	18.0 (15.0-20.0)	18.0 (15.0-20.0)	0.944
Prone iron (seconds)	20.5 (12.0-32.0)	30.0 (13.5-33.5)	0.673
Side iron (seconds)			

Therapeutic Effect of Two Muscle Strengthening Programs in Patients with Patellofemoral Pain Syndrome

Right	15.0 (10.0-21.0)	15.0 (9.5-20.0)	1,000
Left	12.5 (10.5-19.0)	18.0 (11.0-23.0)	0.356
Trunk extension (seconds)	13.5 (6.0-26.5)	13.5 (2.5-20.0)	0,586
Squats	10.0 (8.0-18.5)	12.5 (8.5-20.0)	0.673

* percentage (95% CI); a: U from Mann-Whitney; b: Chi square test

In **Table 6**, with a 95% confidence, the values are expected to oscillate in a narrow range: thus, a statistically significant difference was not found for the domains contemplated by the Kujala test for the two treatment groups, except for the squat domain with a p of 0, 028. However, it can be seen that within the thirteen domains contemplated by the Kujala test, it was found that these results agree with what was found for the total score of the test in the baseline, highlighting that in the pain domain, the "occasionally severe" response option was greater for group B; likewise, they were for the domains of "severe atrophy", "pain with the support of the limb", "going up and down stairs", "sitting with knees bent", especially if you have exercised before, as well as for the most painful movements of the patella with daily activities and severe pain always when running. The score was only greater in group A for the domains of inflammation every night and severe deficiency for knee flexion.

Kujala

Table 6: Distribution of the 13 domains of the Kujala Questionnaire by intervention group in the baseline.

Domain	Treatment A (n = 20) % (95% CI)	Treatment B (n = 20) % (IC95%)	Value p *
Pain			0.506 ^a
Constant and severe	20.0 (7.2-44.3)	20.0 (7.2-44.3)	
Occasionally severe	20.0 (7.2-44.3)	40.0 (20.5-63.2)	
Interferes with sleep	10.0 (2.31-34.2)	10.0 (2.31-34.2)	
Mild and occasional	50.0 (28.3-71.6)	30.0 (13.4-54.1)	
Inflammation			0.108 ^b

Therapeutic Effect of Two Muscle Strengthening Programs in Patients with Patellofemoral Pain Syndrome

Permanently	10.0 (2.31-34.2)	20.0 (7.2-44.3)	
Every night	15.0 (4.5-39.2)	-	
With daily activities	30.0 (13.4-54.1)	10.0 (2.31-34.2)	
After great effort	30.0 (13.4-54.1)	30.0 (13.4-54.1)	
Do not	15.0 (4.5-39.2)	40.0 (20.5-63.2)	
Atrophy			0.451 ^b
Severe	-	5.0 (0.6-30.6)	
Mild	15.0 (4.5-39.2)	25.0 (10.2-49.3)	
Do not	85.0 (60.7-95.4)	70.0 (45.8-86.5)	
Limp			0.890 ^a
Constantly	10.0 (2.31-34.2)	10.0 (2.31-34.2)	

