* Statistical significance p <0.05; a: Chi square test; b: Fisher's exact test

Angle Q and Kujala

Graph 1 shows the correlation between the values of angle Q (right and left) and the total score of the test Kujala obtained in the initial population assessment (baseline), indicating that there is a negative correlation with a coefficient of Spearman's correlation $r = -0.415$ (moderate correlation) for the right Q angle and $r = -0.326$ (slight correlation) for the left Q angle, which means that when the values of the angle Q are greater, the total score in the Kujala test is lower.

Graph 1: Correlation of Q angle values on anterior knee pain with the Kujala test in the baseline.

[figure not shown]

Source: Author.

Angle Q and EVA

In Figure 2 a positive correlation, indicating that as the value of angle Q is greater, the score in the pain measured with a visual analog scale (VAS) is higher for both lower limbs, with a coefficient is observed of Spearman correlation of $r = 0.175$ for the right Q angle and $r = 0.216$ for the left Q angle. It should be noted that although the sample was small, there is a slight correlation.

Graph 2: Correlation of Q angle values on anterior knee pain with EVA in the baseline.

[figure not shown]
Source: Author.

Angle Q - Intervention Groups

In **graphs 3 and 4**, a negative correlation is shown between the values of the angle Q of the right and left knee by treatment groups (A and B) measured at the beginning of the intervention, and the total score obtained in the Kujala test, which indicates that as the angle Q increases, the total Kujala score decreases, with a moderate correlation for group A ($r = -0.545$ right knee) and ($r = -0.548$ left knee) and mild for group B ($r = -0.284$ right knee and $r = -0.173$ left knee).

[figure not shown]
Graph 3: Correlation of the values of the angle Q on the anterior pain of the right knee in the baseline, by treatment groups.

Therapeutic Effect of Two Muscle Strengthening Programs in Patients with Patellofemoral Pain Syndrome

Source: Author.

Graph 4: Correlation of Q angle values on left anterior knee pain in the baseline, by treatment groups.

Source: Author

Angle Q and Muscular Length

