To evaluate the effect of muscle strength on the alignment of the knees and analyze the effect of muscle strength on the unipodal balance, **Table 8** shows the deltas of the medians (changes or differences observed after the intervention) for each of the treatment groups and for each of the variables measured at the beginning and end of the intervention.

In this way, when they include or add exercises for the strengthening of the core, to the traditional treatment of SPF or anterior knee pain, the quality of life measured with the Kujala test in these patients increases, especially by the significant reduction of pain, highlighting for example, that for the total score of the Kujala test, there was a statistically significant difference ($p = 0.025$), with an increase of 5 points for group A (group A = 23.0, group B = 17.0), which indicates that the population of the study group improved their quality of life more after the intervention compared with the people of group B. A similar effect is observed in the increase of the strength of the core musculature for group A, especially in the oblique force evaluated with the side plate, with a difference of 30 seconds for group A, and only five seconds for group B on the left lateral plate, with a statistically significant p value (<0.001).

Therapeutic Effect of Two Muscle Strengthening Programs in Patients with Patellofemoral Pain Syndrome
On the other hand, the differences for the total pain evaluated with EVA were -6 and -4 for group B, with an interquartile range (-10; -4) and (-7; -3) respectively. Although p was not statistically significant, these differences were clinically relevant. For the hip and knee muscle strength, measured with the squat test, there was no statistically significant difference in the median of the deltas between the treatment groups, but there was one in each group, which means that all of them increased strength muscle in hips and knees, as a result of strengthening for these muscle groups.

Table 8: Effect of muscle strengthening on pain, knee alignment, core, hip and knee strength and balance by treatment groups.

Variable	Treatment A			Treatment B			Value p *
	Initial Medium (RI)	Final Medium (RI)	Delta Medium (RI)	Initial Medium (RI)	Final Medium (RI)	Delta Medium (RI)	
Pain (EVA)	7.5 (5.5-9.0)	2 (0-2)	-6 (-10; -4)	7.0 (5.5-8.5)	2.0 (0-4)	-4 (-7; -3)	0.058

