Table 10: Correlation between differences in muscle strength and balance by treatment groups

Therapeutic Effect of Two Muscle Strengthening Programs in Patients with Patellofemoral Pain Syndrome

Variable	Squats	
Balance	Treatment A *	Treatment B *
Right with open eyes	0,558	0.121
Left with open eyes	0,554	0.110
Right with closed eyes	0.390	0.009
Left with closed eyes	0.008	-0.244

* Spearman correlation coefficient.

With the previously stated results, the alternative hypothesis of this study is rejected, which means that adding core exercises to traditional hip and knee muscle strengthening for the treatment of anterior knee pain in patients diagnosed with SPF is more effective in reducing pain and improving the quality of life of these people, they do only hip and knee strengthening exercises.

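### The closing quality-of-life claim rests only on the Kujala score, which the SAP labels in three different ways and whose 13 printed domains are all knee symptoms, signs or physical function

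*SAP*

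**What the plan says.** The final paragraph of the SAP, after Table 10, concludes that program A (core exercises added to hip and knee strengthening) is "more effective in reducing pain and improving the quality of life of these people" compared with hip and knee strengthening alone.

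The only text that links quality of life to a measurement is in the Post-Intervention Results: "the quality of life measured with the Kujala test in these patients increases". That section cites the Kujala total (p = 0.025, median changes 23.0 and 17.0) and attributes the gain mainly to less pain.

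Other sections describe the same score differently:

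- **Bivariate Analysis:** "a comparison of each of the Kujala test domains was initially performed to assess pain in the baseline".
- **Graph 1 title:** "Correlation of Q angle values on anterior knee pain with the Kujala test in the baseline". Graph 2 has the same title with EVA in place of Kujala.
- **Baseline, Study population:** the lower Kujala total in group B is a finding "which indicates better core strength for these patients".

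The outcomes analysed as changes are listed in the Bivariate Analysis: "deltas were generated from the Kujala test, EVA, number of squats, Q angle, balance, physical activity and core strength", with plank and trunk extension given as the core-strength tests.

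**The concern.** A score supports the construct that its items cover. Here one total is called pain in the methods and graph titles, core strength at baseline and quality of life in the results. The last label appears only in the post-intervention text, and it is the one that reaches the conclusion. The SAP gives no reason for reading a knee questionnaire as quality of life.

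At stake is what the trial may be said to have shown. A reader of the last paragraph would credit program A with two patient benefits, less pain and better quality of life. The between-group results in Table 8 show one significant patient-reported difference, on a knee-specific score.

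**Working it through.** No sample size or power figure is involved. The check is a count and a comparison of sections.

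**1. Number of Kujala domains.** Table 6 is titled "Distribution of the 13 domains of the Kujala Questionnaire by intervention group in the baseline". Its headings are: pain, inflammation, atrophy, limp, limb support, walking, stairs, squats, sitting with bent knees, kneecap movements, knee flexion deficiency, running, and jumping (printed as Skip). The count is 13, matching the title.

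**2. What the domains cover.** Every heading is a knee symptom, a sign or a physical function. None concerns emotional, social or overall well-being. Eight use pain wording in the heading or a response option: pain, limb support, stairs, squats, sitting, kneecap movements, running, jumping. The other 13 − 8 = 5 do not: inflammation, atrophy, limp, walking, knee flexion deficiency. On its printed content, the score is neither pure pain nor general quality of life.

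**3. Other candidate measures.** Table 8 is introduced as covering every variable measured at the start and end. Its rows are EVA, Kujala, squats and IPAQ (4), Q angle right and left (2), balance with eyes open and closed on each side (4), prone plank, two side planks and trunk extension (4). That is 4 + 2 + 4 + 4 = 14 rows. None is a separate quality-of-life instrument, and the list of changes in the Bivariate Analysis names none.

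**4. The labels side by side.**

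| Place in SAP | What Kujala stands for |
|---|---|
| Bivariate Analysis; Graph 1 title | pain |
| Baseline, Study population | core strength |
| Post-Intervention Results | quality of life |
| Closing paragraph | quality of life (implied; no other measure is named) |

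The core-strength reading fails on two counts. Core strength has its own rows (planks, trunk extension). And the baseline text takes the lower total (53.0 against 65.5, a gap of 12.5) as better, while the Post-Intervention Results treat a rise in the total as improvement.

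**5. Between-group evidence behind the closing claim.** I take EVA, Kujala and IPAQ as the patient-reported rows. The SAP sets a two-sided alpha of 0.05.

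| Outcome | Median change A | Median change B | p |
|---|---|---|---|
| Kujala | 23.0 | 17.0 | 0.025 |
| EVA | −6 | −4 | 0.058 |
| IPAQ (minutes) | 1539 | 1977 | 0.492 |

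Only Kujala is below 0.05. The pain half of the claim therefore has no significant between-group result on the pain scale itself, as the Post-Intervention Results acknowledge.

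Side note: 23.0 − 17.0 = 6.0, whereas the text gives a difference of 5 points. This needs correcting but does not affect the present point.

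**The case against.** The strongest reply is that the claim is not without a measure. The Post-Intervention Results name Kujala as the quality-of-life measure and give its p-value, so a careful reader can trace the conclusion to its source. This stands: the defect is an unjustified and inconsistent label, not a claim with nothing behind it.

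Four stronger readings are tempting, and the documents do not support them:

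- **That the trial could not answer a quality-of-life objective.** No such objective appears in the available text. The public protocol covers only the intervention, and the theoretical framework it mentions is not included. The absence of an instrument can be stated only for the outcomes listed and tabulated.
- **That Kujala and EVA are the same measurement, so two benefits reduce to one by overlap.** The documents give neither item weights nor a Kujala–EVA correlation, and five domains carry no pain wording. The sound reason for not claiming two benefits is the EVA p-value of 0.058.
- **That Kujala is the only significant patient-reported result.** This is true between groups only. Table 9 gives within-group p-values below 0.001 for EVA in both arms, and 0.029 and 0.012 for IPAQ.
- **That quality of life did not improve.** The data do not speak to this in either direction.

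It can also be said that the documents nowhere define quality of life, so a requirement for emotional or social content comes from outside them. That is fair, and it is why the point is framed as an unjustified reading. The text is plainly translated, so the pain wording in the methods may not be a deliberate definition. That weakens any single label as evidence, but not the disagreement among them.

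**Conclusion.** The point holds as an error of interpretation in the trial's final conclusion. One score carries three labels. None of the 13 domains goes beyond knee symptoms, signs or physical function, and none of the 14 rows in Table 8 is a separate quality-of-life instrument. What Table 8 supports between groups is a larger median rise in the Kujala score with program A (23.0 against 17.0, p = 0.025); it does not support separate benefits on pain and on quality of life.

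No estimate, test or p-value changes. What changes is what the trial may conclude. The finding assumes that Table 6 prints the full domain list, that Table 8 is complete as its introduction says, and that no justification for the quality-of-life reading exists in material that is not public.

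**What to change.** 1. In the Post-Intervention Results and the closing paragraph, replace the quality-of-life wording with *Kujala score (anterior knee symptoms and function)*.
2. State in the conclusion that no separate quality-of-life instrument was analysed.
3. Use that one description of the score in the Bivariate Analysis, the baseline text, the titles of the Kujala graphs, the Post-Intervention Results and the closing paragraph. Delete the core-strength reading at baseline.
4. Rest the between-group conclusion on the Kujala score, report EVA beside it with p = 0.058 as not significant at 0.05, and do not list pain and quality of life as two benefits.

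While that closing sentence is being rewritten, its statement that the alternative hypothesis is rejected should also be reconciled with the superiority claim that follows it.

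The cost is wording only, with no new data or analysis. The downside is a less favourable headline. If the sponsor holds grounds for reading Kujala as quality of life, they would have to be set out in the methods before the label could stay.
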